	Relative Day within a Cycle	≤28	Day 1	Day 15° (± 3)	Day 1 (± 3)	Day 1 (± 3)	Day 30 (± 7)	(± 14)		
Procedure Category	Procedure								Protocol Reference	Instructions
Clinical Tumor Assessment	Tumor measurement (palpable or visible)	Х			See I	nstructions			Section 8.1 and Section 10.3 Appendix 3	 Visible tumor (such as skin lesions) should be documented by photography, and each photographic image of the tumor should include a ruler. If measurable, caliper measurements should be recorded. Images will be collected for central storage for BIRC review Perform at RECIST response assessment intervals outlined below
Tumor Assessment	Radiologic imaging according to RECIST ^b	Х			See I	nstructions			Section 8.1 and Section 10.3 Appendix 3	 Required for all patients Perform according to RECIST v1.1 criteria by the same method used at baseline CT or MRI scan of the chest, abdomen, and pelvis performed with IV contrast when possible^b Response assessments should occur at baseline and then at the following intervals relative to Cycle 1 Day 1: every 8 weeks (±4 days) for the first 12 months and then every 12 weeks (±4 days) thereafter, until radiographic disease progression, death, start of a new anticancer therapy or study completion, whichever occurs first. Perform as scheduled, regardless of any treatment delays or interruptions Perform within 14 days of clinical progression A central radiology vendor will be used to collect and store images for BIRC review

	Study Period	Baseline	Study Treatment (Cycle =28 days)					ontinuation ow-Up		
	Cycle	Screening	1 ar	nd 2	4 and Beyond (if Applicable)		Short-Term Follow-Up ^a	Long-Term Follow-Up ^a		
	Visit	0	1,3	2, 4	5	6 and Beyond (if Applicable)	801	802–8XX		
	Relative Day within a Cycle	≤28	Day 1	Day 15° (± 3)	Day 1 (± 3)	Day 1 (± 3)	Day 30 (± 7)	(± 14)		
Procedure Category	Procedure								Protocol Reference	Instructions

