Tumor Assessment	Bone scintigraphy	X				See Instructions			Section 8.1 and Section 10.3 Appendix 3	 Required for all patients (testing up to 45 days prior to C1D1 may be used for baseline assessment) Postbaseline bone scintigraphy should occur every 24 weeks (±4 days), with first assessment relative to Cycle 1 Day 1, until radiographic disease progression, death, start of a new anticancer therapy, or study completion, whichever occurs first Perform as scheduled, regardless of any treatment delays or interruptions Perform within 14 days of clinical progression Importantly, RECIST v1.1 emphasizes bone scintigraphy is not adequate to measure bone lesions; however, bone scintigraphy can be used to confirm the presence or disappearance of bone lesions A central radiology vendor will be used to collect and store images for BIRC review
Patient Diary (Arms A and C)			Х		X	Х				 Provide patient drug diary on Day 1 of each cycle for patients randomized to Arms A or C. Completed daily by patient Review at each study visit

	Study Period	Baseline	Stu	dy Treatmer	nt (Cycle =	28 days)		ontinuation ow-Up		
	Cycle	Screening	1 ai	1 and 2		4 and Beyond (if Applicable)	Short-Term Follow-Up ^a	Long-Term Follow-Up ^a		
	Visit	0	1,3	2, 4	5	6 and Beyond (if Applicable)	801	802–8XX		
	Relative Day within a Cycle	≤28	Day 1	Day 15° (± 3)	Day 1 (± 3)	Day 1 (± 3)	Day 30 (± 7)	(± 14)		
Procedure Category	Procedure								Protocol Reference	Instructions
Survival Information							Х	Х	Section 8.1 and Section 10.3 Appendix 3	 Survival information is collected during both study treatment and at post-discontinuation follow-up During long-term follow-up, survival information is collected approximately every 12 weeks (±14 days) for the duration of this period. Survival information may be collected in clinic or by contacting the patient or family directly (for example, via telephone). Long-term follow-up data collection may include post-discontinuation anticancer therapies. Date of progression on the FIRST post-discontinuation anticancer treatment should be collected.

	Study Period	Baseline	Stu	dy Treatmer	nt (Cycle =	28 days)		ontinuation ow-Up		
	Cycle	Screening	1 a	nd 2	3	4 and Beyond (if Applicable)	Short-Term Follow-Up ^a	Long-Term Follow-Up ^a		
	Visit	0	1,3	2, 4	5	6 and Beyond (if Applicable)	801	802–8XX		
	Relative Day within a Cycle	≤28	Day 1	Day 15° (± 3)	Day 1 (± 3)	Day 1 (± 3)	Day 30 (± 7)	(± 14)		
Procedure Category	Procedure								Protocol Reference	Instructions

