8.1.2. Efficacy Assessments during Post-discontinuation Follow-Up

Post-discontinuation follow-up during the study period will be conducted as described in the SoA (Section 1.3). For those patients who are randomized and never receive study treatment or those who discontinue study treatment without objectively measured PD, the investigative sites will continue to monitor patients and periodically evaluate tumor response approximately every 8 weeks for the first 12 months with the first assessment relative to Cycle 1 Day 1 and thereafter approximately every 12 weeks by the same method used at baseline and throughout the study until the patient has objective disease progression, death, start of a new anticancer therapy or study completion. In addition, anticancer therapies initiated after study treatment discontinuation will be collected during this follow-up period.

After the patient has objective disease progression, radiologic imaging and photographic images are no longer required and the patient will be followed up approximately every 12 weeks until the patient's death or overall study completion. Lilly will continue to collect survival data on all patients but may reduce data collection for other efficacy data. Sponsor will notify investigators when this reduced data collection can begin.

Tumor assessments will be performed for each patient at the times shown in the SoA (Section 1.3).

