9.4.7. Other Analyses

9.4.7.1. Exploratory Analyses

All the exploratory analyses will be conducted for each comparison (Arm A versus Arm B in the ITT and the *ESR1*-mutation detected populations and Arm C versus Arm A in the ITT population) per the prespecified analysis populations, unless otherwise stated.

Time to progressive bone metastases is defined as the time from randomization to the date of earliest development of new bone metastases. Time to progressive bone metastases will be summarized for each treatment arm using the Kaplan-Meier method and will be compared between 2 arms using the log-rank test.

Time to first SRE is defined as the time from randomization to the first SRE event defined as either pathological fracture, spinal cord compression, radiation to the bone, or surgery to the bone. Time to first SRE will be summarized for each treatment arm using the Kaplan-Meier method and will be compared between 2 arms using the log-rank test.

Time to chemotherapy is defined as the time from randomization to the initiation of first postdiscontinuation chemotherapy. TTC will be summarized for each treatment arm using the Kaplan-Meier method and will be compared between 2 arms using the log-rank test.

Chemotherapy-free survival is defined as the time from randomization to the initiation of first postdiscontinuation chemotherapy or death, whichever is earlier. CFS will be summarized for each treatment arm using the Kaplan-Meier method and will be compared between 2 arms using the log-rank test.

Progression-free survival 2 is defined as the time from randomization to disease progression on the next line of treatment or death, whichever is earlier. PFS2 will be summarized for each treatment arm using the Kaplan-Meier method and will be compared between 2 arms using the log-rank test.

Time to worsening of ECOG PS of ≥ 2 is defined as the time from randomization to the date when ECOG PS score of ≥ 2 was observed for the first time. Time to worsening of ECOG PS of ≥ 2 will be summarized for each treatment arm using the Kaplan-Meier method and will be compared between 2 arms using the log-rank test.

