4.5. Exploratory Endpoints Analysis

All the exploratory analyses will be conducted for each comparison (Arm A versus Arm B and Arm C versus Arm A) per the prespecified analysis population for each comparison if the number of events is sufficient, unless otherwise stated.

Time to progressive bone metastases is defined as the time from randomization to the date of earliest development of new bone metastases or unequivocal progression of current bone lesions. Participants not known to have progressive bone metastases will be censored at the date of last documented tumor assessment. Time to progressive bone metastases will be summarized for each treatment arm using the Kaplan-Meier method and will be compared between 2 arms using the log-rank test.

Time to first skeletal-related event (SRE) is defined as the time from randomization to the first SRE defined as either pathological fracture, spinal cord compression, radiation to the bone, or surgery to the bone. Participants not known to have an SRE will be censored at the date of last documented assessment. Time to first SRE will be summarized for each treatment arm using the Kaplan-Meier method and will be compared between 2 arms using the log-rank test.

Time to chemotherapy (TTC) is defined as the time from randomization to the initiation of first post-discontinuation chemotherapy. Participants who die prior to the initiation of chemotherapy will be censored at the date of death. TTC will be summarized for each treatment arm using the Kaplan-Meier method and will be compared between 2 arms using the log-rank test.

Chemotherapy-free survival (CFS) is defined as the time from randomization to the initiation of first post-discontinuation chemotherapy or death, whichever is earlier. Participants not known to have initiated chemotherapy will be censored at the last documented assessment. CFS will be summarized for each treatment arm using the Kaplan-Meier method and will be compared between 2 arms using the log-rank test.

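### Kaplan-Meier for time to progressive bone metastases censors competing events, so the curve read as a proportion overstates how many participants have bone progression

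*SAP*

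**What the plan says.** **Event.** SAP Section 4.5 counts "the date of earliest development of new bone metastases or unequivocal progression of current bone lesions". Protocol Section 9.4.7.1 is narrower: "Time to progressive bone metastases is defined as the time from randomization to the date of earliest development of new bone metastases". Death is not an event in either document.

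**Censoring.** The protocol gives no rule for this endpoint. The SAP rule is "Participants not known to have progressive bone metastases will be censored at the date of last documented tumor assessment". It covers participants whose first progression is outside bone and participants who die, with no separate provision for either.

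**Summary and test.** Protocol Section 9.4.7.1 says "Time to progressive bone metastases will be summarized for each treatment arm using the Kaplan-Meier method", with a log-rank comparison between two arms, and SAP Section 4.5 says the same. Neither document names a cumulative incidence or other competing-risk method for this endpoint.

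**Imaging.** In the Schedule of Activities (Protocol Section 1.3), RECIST imaging is 8-weekly for the first 12 months and continues "until radiographic disease progression, death, start of a new anticancer therapy or study completion, whichever occurs first". Bone scintigraphy is 24-weekly with the same stopping events. Protocol Section 8.1.2 adds: "After the patient has objective disease progression, radiologic imaging and photographic images are no longer required".

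**The concern.** A new bone lesion, or unequivocal worsening of existing bone lesions, is itself a RECIST progression (Protocol Section 8.1.3 and Appendix 3). Because required imaging ends at the first radiographic progression anywhere, the endpoint is close to one component of PFS. The other components are first progression outside bone and death. The first normally ends observation for bone progression; the second always does.

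Kaplan-Meier treats a censored participant as someone who would go on to have the event at the same rate as those still being scanned. Applied to participants who have progressed in liver or lung, or who have died, this adds bone progressions that are never observed. The curve then no longer estimates the share of participants with bone progression.

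The arm with shorter PFS loses more participants to other events, so for a given bone share its overstatement is larger. The gap between the curves is then not the gap in the share of participants affected.

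**Working it through.** **1. Inputs from the plan.** The plan states no figure for the bone endpoint, so the check starts with the PFS figures it builds on (SAP Section 5).

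- Arm B median 4.3 months and HR 0.74: 4.3/0.74 = 5.81, a gain of 1.5 months, as stated.
- Arm A median 5.8 months and HR 0.7: 5.8/0.7 = 8.29, a gain of 2.5 months, as stated. The Arm C median is therefore about 8.3 months.
- Power for 480 events, HR 0.74, 1-sided alpha 0.005: 76.5% by Schoenfeld's formula, against a stated 76%.

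**2. Assumptions not in the documents.** PFS times are exponential, and a constant share f of first PFS events involves bone. The range examined is f = 20-50%, with 10% as a low case.

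**3. Formulas.** Let L = ln 2 / median PFS.

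- Kaplan-Meier complement with other events censored: 1 − exp(−f·L·t)
- Actual share with bone progression (cumulative incidence): f·(1 − exp(−L·t))

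For Arm B, L = 0.693/4.3 = 0.1612 per month. At t = 12 and f = 0.5, the complement is 1 − exp(−0.967) = 62.0% and the share is 0.5 × (1 − exp(−1.934)) = 42.8%. The difference is 19.2 points.

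**4. Results at 12 months** (Kaplan-Meier complement / cumulative incidence = overstatement in points):

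| f | Arm B (4.3 mo) | Arm A (5.8 mo) | Arm C (8.3 mo) |
|---|---|---|---|
| 10% | 17.6 / 8.6 = 9.0 | 13.4 / 7.6 = 5.7 | 9.6 / 6.3 = 3.2 |
| 20% | 32.1 / 17.1 = 15.0 | 24.9 / 15.2 = 9.7 | 18.2 / 12.7 = 5.5 |
| 30% | 44.0 / 25.7 = 18.4 | 35.0 / 22.9 = 12.1 | 26.0 / 19.0 = 7.0 |
| 40% | 53.9 / 34.2 = 19.7 | 43.7 / 30.5 = 13.2 | 33.1 / 25.3 = 7.7 |
| 50% | 62.0 / 42.8 = 19.2 | 51.2 / 38.1 = 13.1 | 39.5 / 31.7 = 7.8 |

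Differences are taken before rounding. A simulation with independent censoring of 2% per month, run at f = 20% and 50%, agreed within 0.2 points. At 6 months the gaps for Arms A and B at f = 20-50% are about 3-7 points. In the *ESR1*-mutation detected subset, the Arm B median of 3.6 months gives 19-24 points at 12 months.

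**5. Scans every 8 weeks.** With an interval of 56/30.4375 = 1.84 months, h = 1 − exp(−1.84·L) and six scans to week 48, the complement is 1 − (1 − f·h)^6 and the share is f·(1 − (1 − h)^6). For f = 20-50% the overstatement is 10.5-14.6 points (Arm B), 6.8-9.8 (Arm A) and 3.9-5.7 (Arm C).

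**6. Against sampling error.** The share remaining progression-free at 12 months is exp(−12·L): 14% in Arm B and 24% in Arm A, or about 46 and 76 of 320. Greenwood's standard error for the Kaplan-Meier estimate is then about 3.4-4.1 points at f = 20-50%. In continuous time the overstatement in Arms A and B exceeds this throughout that range.

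**7. Gap between Arms B and A at 12 months.** At f = 50%, Kaplan-Meier shows 62.0 − 51.2 = 10.8 points and cumulative incidence 42.8 − 38.1 = 4.7. At f = 20% the gaps are about 7 and 2 points.

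**The case against.** **The size is conditional.** A reader might take 10-19 points as what the curve will overstate. The documents do not support that. They give no bone share, and 10-19 describes only ITT Arms A and B, in continuous time, at a 20-50% share. Arm C, which is also analysed, falls below it, as do Arms A and B at a 10% share. A low share is plausible under the protocol's narrower event. This objection stands, and the size has to be stated with its conditions.

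**Later bone progression is not impossible to record.** A reader might infer that a first non-bone progression rules it out. Imaging is then no longer required, but it is not forbidden, and Protocol Sections 6.1.1 and 7.1 allow some treatment beyond progression. Nor does the SAP say that later bone findings are ignored. This softens the effect without removing it, because scheduled imaging normally stops.

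**The treatment comparison is not invalid.** With equal bone shares, the bone-specific hazard ratio in this model really is 0.74, and the log-rank test compares exactly those hazards. Cumulative incidence is not neutral either: it converges to the same plateau in both arms because the worse arm loses more participants to other events. The two summaries answer different questions. That supports adding cumulative incidence and labelling the rest; it does not support dropping the log-rank test.

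**No median or landmark rate is promised.** The SAP specifies those for PFS and OS, not here. The objection is to any reading of this curve as a proportion.

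**The stakes are low.** The endpoint is exploratory, lies outside the graphical testing procedure, and is analysed only if events suffice. SAP Section 4.1 allows alternative methods when assumptions fail, but that clause is generic and names nothing for this case. By contrast, SAP Section 4.6 adds sensitivity analyses counting death for pain and physical function, and Section 4.5 pairs time to chemotherapy with chemotherapy-free survival. The bone endpoint has no such companion.

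**Conclusion.** The point holds as a low-severity matter of estimator and labelling. Competing events are censored as if uninformative, and nothing else in the plan corrects this for the bone endpoint. The direction follows from the formulas: one minus Kaplan-Meier exceeds the share of participants with bone progression.

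The size rests on exponential times, the plan's ITT medians and an assumed bone share of 20-50%. Under these, the 12-month overstatement is about 15-20 points in Arm B, 10-13 in Arm A and 5.5-8 in Arm C. It is about 7-15 points for Arms A and B on the 8-weekly scan grid, and about 9 (B) and 6 (A) in continuous time at a 10% share.

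The log-rank comparison stands as a cause-specific one, and no primary or key secondary conclusion is affected.

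**What to change.** In SAP Section 4.5:

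1. Report the proportion with bone progression by Aalen-Johansen cumulative incidence, with first progression outside bone and death without bone progression as competing events.
2. Keep the log-rank test, and any Kaplan-Meier display, labelled as cause-specific.
3. Align the event definition with Protocol Section 9.4.7.1, so that both documents either include or exclude unequivocal progression of existing bone lesions.

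The cost is SAP wording and a standard procedure, plus a matching edit if the protocol's definition is the one changed. No new data and no alpha are needed. The downside is that reported rates will be lower than the Kaplan-Meier figures.

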Breast cancer is the most frequent cancer among women and is a major cause of cancer-related deaths worldwide. It is estimated that more than 2 million new cases of breast cancer occurred worldwide in women in 2018 (Bray et al. 2018). Treatment options for women with breast cancer are largely determined by tumor hormone receptor (HR) and HER2 status (Gradishar et al. 2020; Waks and Winer 2019).

Over two-thirds of breast cancers express the ER, which is a key driver of breast cancer initiation and progression. ER+ mBC is incurable and therefore considered a serious and life-threatening disease, with a median OS of only 2 to 3 years (Cardoso et al. 2012; Sledge 2020). For patients with HR+, HER2- status, treatment options include ET given alone or in combination with a CDK4/6 inhibitor (abemaciclib, palbociclib, ribociclib); an mTOR inhibitor (everolimus), or a PI3K inhibitor (alpelisib, for the subset of tumors also harboring select PIK3CA mutations). Alternatively, some patients may receive chemotherapy (for example, capecitabine, docetaxel, paclitaxel, nab-paclitaxel (Waks and Winer 2019; Gradishar et al. 2020) as initial therapy based on aggressiveness at initial presentation, or as salvage therapy following failure of ET-based interventions. However, in most ER+ breast cancers, ER remains an important therapeutic target even after the development of resistance to initial ET and changing the ET backbone has led to improved outcomes, either alone or with other anticancer therapies (Weatherman et al. 1999; Baselga et al. 2012; Turner et al. 2015; Finn et al. 2016; André et al. 2019).

Multiple means of inhibition of ER signaling are already available. These include strategies such as direct ER modulation (tamoxifen), systemic prevention of the conversion of androgens to estrogens using AIs, and SERDs (fulvestrant) that block and degrade the ER. While ET is typically highly effective initially, especially with the incorporation of CDK4/6 inhibitors (Finn et al. 2016; Hortobagyi et al. 2016; Goetz et al. 2017), most patients ultimately relapse and develop acquired ET resistance (Lei et al. 2019). Outcomes for subsequent second-line ET, often with fulvestrant or exemestane, are unfortunately poor and remain an area of unmet need (Chia et al. 2008).

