2.1. Multiplicity Adjustment

To adjust for multiplicity and control, the overall type I error rate at 0.025 (1-sided), a graphical approach (Bretz et al. 2009; Mauer and Bretz 2013) will be used to test the 3 PFS primary endpoints and the 3 key secondary overall survival (OS) endpoints. Besides, the Lan-DeMets stopping boundaries (O'Brien-Fleming type) will be used to derive the boundaries for the interim and final analyses for PFS and OS in order to control the Type I error rate. Further details are provided in Section 4.3.3.

3. Analysis Populations

For the purposes of analysis, the following analysis populations are defined:

Population	Description	
ITT	All participants randomly assigned to study treatment, regardless of whether they take any doses of study treatment, or if they took the correct treatment. Participants will be analyzed according to the treatment group to which they were assigned. The full ITT population is all participants randomly assigned to study treatment, regardless of concurrent enrollment or not.	
Safety	All participants randomly assigned to study treatment and who take at least 1 dose of study treatment. Participants will be analyzed according to the study treatment they actually received.	
ORR Evaluable	The subset of participants from the ITT population who have measurable disease per RECIST v1.1 at baseline.	
Per-protocol (PP)	All randomized participants (ITT population) who do not have important protocol deviations (IPD) that could potentially affect the efficacy conclusions of the study. See Section 6.2 for details.	
Analysis Population for Arm A vs Arm B in the ITT population	All participants randomized to Arm A and Arm B (N = approximately 640)	
Analysis Population for Arm A vs Arm B in the ESR1 -mutation detected population	The subset of participants with ESR1 mutation detected in the analysis population for Arm A versus Arm B in the ITT population	
Analysis Population for Arm C vs Arm A in the ITT population	Participants concurrently randomized to Arm A and Arm C (N = approximately 440)	

Abbreviations: ITT = intention-to-treat; N = total number of participants; ORR = objective response rate; OS = overall survival; PFS = progression-free survival; RECIST 1.1 = Response Evaluation Criteria in Solid Tumors, version 1.1.

The ITT population is used to analyze endpoints related to the efficacy objectives, and the safety population is used to analyze the endpoints and assessments related to safety.

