4.4.1.3. Interim Analyses for OS Endpoints

For OS between Arm A and Arm B in the ITT population, the following analyses are planned:

OS look 1	At the time of final analysis of PFS between Arm A vs Arm B in the ITT population
OS look 2	Approximately 255 OS events
OS look 3	Approximately 330 OS events
Final OS	Approximately 390 OS events (estimated to be 3 years after the final analysis of PFS)
A11	

Abbreviations: ITT = intention-to-treat; OS = overall survival; PFS = progression-free survival.

The first OS analysis will be conducted at the time of final analysis of PFS between Arm A vs Arm B in the ITT population if PFS is significant. According to the graphical approach, if PFS (H₁) is not significant after the final analysis, OS (H₄) will not be statistically evaluated. The Lan-DeMets spending function (O'Brien-Fleming type) will be used to determine the boundaries for the interim and final analyses of OS, specifically

$$\alpha^*(t_k) = 2\left(1 - \Phi\left(\frac{\Phi^{-1}(1 - \alpha/2)}{\sqrt{t_k}}\right)\right),$$

where t_k is the information fraction at time k, Φ is the standard normal cumulative distribution function, and Φ^{-1} is the standard normal quantile function. The p-value boundary at each analysis is summarized in Table 4.1 assuming OS for Arm A versus Arm B in the ITT population will be tested at the alpha level of 0.00693978, which is the alpha level assuming all PFS hypotheses H₁, H₂ and H₃ are rejected. The actual boundaries will be updated based on observed number of events and the actual alpha level that is passed to H₄ from previous tests, using software (e.g., EAST version 6.5).

Table 4.1.	Stopping Boundaries for Each OS Analysis Between Arm A and Arm B in the ITT
	Population for Illustration

Analysis	Critical P-value Boundary	Critical HR Boundary	Cumulative Type I Error Rate
OS look 1	1.4E-05	0.504	1.4E-05
OS look 2	0.0008	0.675	0.0008
OS look 3	0.0031	0.740	0.0033
Final OS	0.0059	0.775	0.0069

Abbreviations: ITT = intention-to-treat; OS = overall survival.

For OS between Arm A and Arm B in the *ESR1*-mutation detected population (H₅), the following analyses are planned assuming that the final analysis for Arm A versus Arm B in the ITT population and the final analysis for Arm A versus Arm B in the *ESR1*-mutation detected population occur at the same time.

OS look 1	At the time of final analysis of PFS between Arm A vs Arm B in the ITT population
OS look 2	At the time of OS look 2 in ITT

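### Time to chemotherapy is summarized by Kaplan-Meier with deaths censored, so its curve, rates and medians overstate how many participants have started chemotherapy by a given time if read that way

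*SAP*

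**What the plan says.** SAP 4.5 gives the definition: "Time to chemotherapy (TTC) is defined as the time from randomization to the initiation of first post-discontinuation chemotherapy". Death is not an event. The rule for it is explicit: "Participants who die prior to the initiation of chemotherapy will be censored at the date of death". The analysis is standard: "TTC will be summarized for each treatment arm using the Kaplan-Meier method and will be compared between 2 arms using the log-rank test". Protocol 9.4.7.1 has the same event and the same methods, without a rule for death.

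The same SAP section also plans a composite: "Chemotherapy-free survival (CFS) is defined as the time from randomization to the initiation of first post-discontinuation chemotherapy or death, whichever is earlier". SAP 4.8.5 separately tabulates how many participants receive anticancer treatment after study treatment, by type, drug class and line. Neither document plans a competing-risk estimate for TTC.

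TTC is listed as exploratory in both documents. It is outside the six hypotheses of the testing graph (SAP 4.3.3), and SAP 4.5 makes the exploratory analyses conditional on there being enough events.

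**The concern.** Death before chemotherapy is a competing event, because it makes later chemotherapy impossible. Kaplan-Meier treats a participant censored at death like one who is alive and still under observation, and passes that participant's remaining probability to the survivors. The curve then describes chemotherapy use in a hypothetical setting where nobody dies first, and that only if the two processes are independent.

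Delay of chemotherapy matters to patients, and a 12- or 24-month rate or a median read off this curve is easily reported as the share who had started chemotherapy by then. Death is common enough here to matter. Protocol Section 2 describes the disease as one "with a median OS of only 2 to 3 years", and the SAP plans for about 390 deaths among about 640 participants in Arms A and B, or 61%.

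**Working it through.** The documents state no TTC rate, median or event count, so there is no figure for this endpoint to reproduce.

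**Anchor for mortality.** SAP 4.4.1.3 plans OS looks at about 255, 330 and 390 deaths. Its spending function at alpha 0.00693978 gives cumulative alpha of 0.0008, 0.0033 and 0.0069, which matches SAP Table 4.1. The look 1 boundary of 1.4E-05 implies about 150 deaths at final PFS. Going from about 150 to 390 deaths among 640 over 3 years, ignoring dropout, gives

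ln[(640 − 150)/(640 − 390)]/36 = 0.0187 deaths per month,

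a median OS of about 37 months. At that rate 1 − exp(−24 × 0.0187) = 36.1% have died by 24 months. The 2- to 3-year median in the protocol corresponds to ln 2/24 = 0.0289 down to ln 2/36 = 0.0193 per month.

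**Overstatement within an arm.** Let hc be the hazard of chemotherapy and hd the hazard of death before chemotherapy, both constant. These values are assumptions; the documents give neither.

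- One minus Kaplan-Meier: 1 − exp(−hc·t)
- Proportion who have started chemotherapy: hc/(hc + hd) × [1 − exp(−(hc + hd)·t)]
- Proportion who have died first: the same expression with hd in the numerator

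With hc = 0.03 and t = 24, one minus Kaplan-Meier is 1 − exp(−0.72) = 51.3%, whatever hd is.

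| hd per month | Started chemotherapy | Overstatement (points) | Died first | Month when half have started |
|---|---|---|---|---|
| 0.005 | 48.7% | 2.6 | 8.1% | 25.0 |
| 0.01 | 46.3% | 5.0 | 15.4% | 27.5 |
| 0.02 | 41.9% | 9.4 | 28.0% | 35.8 |

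The Kaplan-Meier median is ln 2/0.03 = 23.1 months in every row.

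The last row uses hd = 0.02, slightly above the 0.0187 implied for all deaths. Set against 36.1% dead by 24 months, 28.0% dying first means that 28.0/36.1, or 78%, of deaths precede chemotherapy.

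**Sensitivity.** With a chemotherapy median of 18 months, a median OS of 36 months and hd at half the overall death hazard, the 24-month figures are 60.3% against 54.8%, or 5.5 points. A simulation of 400,000 participants gave 60.4% and 54.9%. Over chemotherapy medians of 12 to 24 months, median OS of 24 to 37 months and hd at 10% to 100% of the overall death hazard, the overstatement at 24 months runs from 1.0 to 16.7 points. The top combines the fastest chemotherapy, the shortest OS and the full death hazard.

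**Difference between arms, equal mortality.** Assume a chemotherapy hazard ratio of 0.74, so hc is 0.03 and 0.0222. One minus Kaplan-Meier gives 51.3% − 41.3% = 10.0 points at 24 months. Cumulative incidence gives 9.6, 9.2 and 8.4 points for hd = 0.005, 0.01 and 0.02. The distortion is 0.4, 0.8 and 1.6 points.

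**Difference between arms, unequal mortality.** Keep hc = 0.03 in both arms and let hd be 0.01 in one and 0.02 in the other. Kaplan-Meier shows 51.3% in both. The proportions who have started are 46.3% and 41.9%, a gap of 4.4 points that Kaplan-Meier does not show.

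**The case against.** The strongest reply is that neither document says that one minus Kaplan-Meier will be read as the share starting chemotherapy. Death is censored openly, and a composite that counts death sits beside TTC, which looks like a deliberate pair. That stands: the plan is wrong only under a particular reading. The reading is a natural one, though, and the composite does not separate chemotherapy from death.

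A reader might infer that the comparison between arms is invalid. The documents do not support that. With deaths censored, the log-rank test compares cause-specific chemotherapy hazards and is valid for that purpose. Nor does a 3- to 9-point overstatement within an arm carry over to the difference between arms; with equal mortality most of it cancels.

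A reader might also infer that the trial will report no real proportion receiving chemotherapy. SAP 4.8.5 supplies one. It is a crude percentage with no time scale, so it limits the gap without closing it.

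A third inference is that time to first skeletal-related event (SRE) is affected to the same degree. Its rule is "Participants not known to have an SRE will be censored at the date of last documented assessment", which handles death only implicitly. The protocol's schedule of activities collects these events only through short-term follow-up, and no size has been shown for that endpoint.

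Finally, cumulative incidence has its own trap. In the unequal-mortality example, the arm with more deaths shows 4.4 points less chemotherapy, which could pass for chemotherapy avoided. This stands, and it shapes the fix.

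**Conclusion.** The point holds as one of estimation and labelling on an exploratory endpoint. The direction is certain: if any participant dies before chemotherapy, the Kaplan-Meier curve, rates and median overstate how many have started and how soon.

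The size is not certain. About 3 to 5 points per arm at 24 months rests on constant hazards of 0.03 for chemotherapy and 0.005 to 0.01 for death before it. About 9 points at the same chemotherapy hazard requires a pre-chemotherapy death hazard as high as the all-death hazard implied by the SAP's OS plan, so that the great majority of deaths come first. A median OS nearer 2 years would make that less extreme.

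The between-arm distortion is about 0.4 to 1.6 points under equal mortality and an assumed chemotherapy hazard ratio of 0.74. It becomes material only if pre-chemotherapy mortality differs by arm. The alpha-controlled tests are untouched.

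**What to change.** In SAP 4.5, summarize TTC with Aalen-Johansen cumulative incidence curves for chemotherapy, with death before chemotherapy as the competing event. Show them together with the cumulative incidence of death before chemotherapy and with chemotherapy-free survival. Keep the log-rank test, labelled as a comparison of cause-specific chemotherapy hazards. Add a sentence that lower chemotherapy incidence in an arm with more early deaths is not to be read as benefit.

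The same display for time to first SRE is optional.

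The cost is SAP wording and a standard procedure. Protocol 8.1.2 already provides for collecting later anticancer therapies and survival, so no new data are needed. One drawback is that medians may not be reached: under constant hazards the incidence can never exceed hc/(hc + hd), so it does not pass 50% when death before chemotherapy is at least as frequent as chemotherapy.
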